Initiated in the orthopaedic literature, a new technique of wound dressing has been described to reduce SSI¹¹. Incisional negative pressure wound therapy (NPWT) using devices such as the Prevena™ involves applying a wound vacuum sponge over a standard wound closure (including fascial closure and skin closure with staples). The incisional NPWT dressing is then left in place for 5 to 7 days before removal. A recent retrospective study by Bonds *et al.* described the ability of incisional NPWT to reduce SSI rates in open colorectal surgery from 29.3-12.5%¹².

The aim of the current study is to assess the clinical effectiveness of incisional NPWT to reduce SSI rates in open, re-operative colorectal surgery. The primary endpoint of this study is the occurrence of superficial SSI within 30 days after surgery and the secondary endpoints include, length of hospital stay and cost effectiveness.

Methods

Study design and patients

This investigator-initiated trial will be a prospective, unicentre, randomized controlled trial. It is planned to be conducted from July 2015 to June 2018 at the Department of Colorectal Surgery at the Cleveland Clinic, Ohio. However, it is likely given the high volume practice of department, that

it will be completed sooner. Patients aged over 18 years undergoing re-operative colorectal surgery defined as the excision or revision of a prior anastomosis, intestinal resection with an incisional hernia repair or enterocutaneous fistula repair in both elective and emergency settings are eligible for enrolment. Patients undergoing completion proctectomy and ileal pouch anal anastomosis with a mucous fistula from their rectal stump will also be included. Laparoscopic or laparoscopic assisted procedures, patients who had undergone a laparotomy within the preceding three months and an active SSI at the time of surgery will be excluded. Institutional review board approval will be sought before trial commencement, written informed consent will be obtained from all patients before enrolment and the trial will be registered with clinicaltrials.gov. The number and reason of patients excluded and lost to follow-up will be prospectively recorded.

Randomization

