Enrolled patients will be randomly assigned through a concealed centralized secure web based system in a 1:1 ratio to either the control arm (standard post-operative care) or the intervention arm (the application of the Prevena™ NPWT system (Acelity, San Antonio, TX)). Randomization will be performed when the patient attends the last preoperative visit using the REDCap™ (Research Electronic Data Capture) secure online system. In our department this visit occurs on the day prior to surgery, facilitating ease of enrolment.

The departmental SSI prevention bundle will be used in all cases including preoperative mechanical bowel preparation with the addition of oral antibiotics, a preoperative patient shower with Hibiclens (Mölnlycke Health Care, Norcross, GA), intravenous antibiotics administered 1 hour before skin incision, antiseptic preparation of the abdomen, the routine use of a wound protector, surgical glove changes following contamination and before wound closure and separate instruments used for wound closure. The non-NPWT dressing will be left in place for 48 hours before changing.

Surgeons in the Colo-rectal surgery department trained in the application of the Prevena™ NPWT system will enroll and operate on patients included in this trial. All wounds will be irrigated with sterile saline before closure and the attending staff surgeon will perform all closures themselves. The fascia will be closed with interrupted or running # 1 Maxon™ (Covidien), followed by skin closure with staples. Control patients with standard wound dressings will have gauze and tape dressings applied while those in the NPWT group will have the Prevena™ system applied; both before the maturation of the ostomy to avoid contamination of the wound with enteric content. The Prevena™ system will remain in place for 7 ± 1 days. However, if concern exists for the patients wound, it will be removed, the wound assessed and this will be recorded as a break from trial protocol. The Prevena™ will however be reapplied if the wound is not infected.

Efficacy outcomes

The primary endpoint will be the occurrence of superficial surgical site infection within 30 days after the operation. Diagnosis will be based on criteria developed by the Centers for Disease Control (CDC)¹³. All wound assessors will be experienced in the appraisal of postoperative wounds and will be provided with standardized criteria and instruction regarding assessment.

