Secondary endpoints will include length of hospital stay, cost effectiveness, and the clinical efficacy of the device in relation to the degree of contamination, patient comorbidity, and operative demographics. This information will be recorded contemporaneously on standardized clinical

report forms. Data for this study will then be entered into a REDCap database, which uses a MySQL database via a secure web interface with data checks used during data entry to ensure data quality. REDCap includes a complete suite of features to support HIPAA compliance, including a full audit trail, user-based privileges, and integration with the institutional LDAP server. The MySQL database and the web server will both be housed on secure servers operated by the Cleveland Clinic.

Procedures

Preoperative evaluation will include the prospective assessment and recording of demographic data related to the patient and their co-morbidities. Operative details, including any deviation from allocation, will be recorded immediately after the operation (Appendix 1). The post-operative wound will be assessed daily by the attending staff surgeon. A trained reviewer independent from the surgical team performing the intervention will formally assess the wound on post-operative day seven. If the patient is discharged prior to post-operative day 7, an early outpatient assessment will be scheduled for day 7 ± 1 day as is the standard practice of our department. A second formal wound review will be performed at 30 (+/-7) days, which will involve the patient returning to hospital for a physical review of the wound. At this same visit, patients will also complete a supervised, self-reported post-discharge questionnaire (PDQ) with the study investigator to identify any occurrence of SSI during the intervening period between the two clinical assessments. The questionnaire is based on the validated Health Protection Agency surgical site infection surveillance system⁶, which is based on the original CDC definitions (Appendix 2) and has been used in prior high quality randomized trials of SSIs⁶. To our knowledge, this will represent the first time this questionnaire is used in a trial of Prevena™. On day 7 ± 1 day and 30 \pm 7 days a photograph will be taken of the wound to be evaluated by a blinded assessor of wound healing at a later date and scored on a modified 10-point Likert scale (1 = very poorly healed; 10 = fully healed).

Cost Analysis

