The objective of the economic evaluation is to explore the relative cost-effectiveness of Prevena™ NPWT compared to standard care. Cost and resource use data will be collected prospectively for both arms of the trial. Trial co-coordinators will identify hospital utilization items and primary care utilization items will be determined by patient interview at the post-operative 30-day clinic visit. Unit costs will be valued in \$ (2015 value). The cost of the intervention (Prevena™ NPWT) will be obtained from the manufacturer. Inpatient care resource items will be sourced from the Cleveland Clinic Reference Costs data. Total resource costs will be obtained by summation of the individual resource costs for each category of resource item accessed by trial patients. Individual resource costs will be obtained by multiplying the resource use by the corresponding unit costs.

Statistical analysis

We hypothesize that the use of Prevena™ incisional NPWT in adults reduces SSI rates in open, re-operative colorectal surgery. For re-operative colorectal surgery, the Department of Colorectal Surgery at the Cleveland Clinic, Ohio has observed a 19.4% overall SSI rate (unpublished internal audit). Assuming a 2.34 fold reduction in SSI rates based on a prior retrospective study in the setting of Colorectal Surgery¹² (19.4% to 8.3%), 298 patients (149 per control and intervention arm) are required to achieve a power of 80% and a two-sided type I error rate of 0.05 (StudySize v3.0, CreoStat HB, Gothenburg, Sweden). As there is only one primary endpoint (SSI development), adjustments for multiplicity are not required.

Results will be analyzed according to the intention to treat principal. For the primary endpoint,

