missing data will be handled by the principal of complete-case analysis, thus, participants with missing data will be excluded from the analysis. Descriptive statistical comparisons between the two study groups will be performed with the use of chi-square tests or Fisher's exact test, as appropriate, for categorical end points and analysis-of-variance techniques or Wilcoxon rank-sum tests, as appropriate, for continuous end points. The log-rank tests will be used to compare the time to first surgical-site infection between the two study groups. Kaplan–Meier survival estimates of the time to first surgical-site infection will also be calculated. Analyses will be performed with SPSS version 20.0 (IBM Corp, Armonk, NY, USA). $P<0.05$ will be considered statistically significant. A formal, interim analysis is planned to take place when a total of one hundred patients have been accrued for both arms all together.

References

1. de Lissovoy G, Fraeman K, Hutchins V, et al: Surgical site infection: incidence and impact on hospital utilization and treatment costs. *Am J Infect Control* 37:387-97, 2009
3. Burke JP, O'Connell PR: Surgical site infection and colorectal surgery: a research priority. *Dis Colon Rectum* 57:e390, 2014

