Appendix 1: Perioperative clinical variables recorded.

Pre-operative Factors
Age
Sex
Body mass index (Kg/M ²)
Charleson co-morbidity index
Diabetic
Current smoker
Chronic kidney disease
Medications:
-Steroids
-Immunosuppressants
Preoperative serum albumin
Pathology
-Malignancy
-Inflammatory bowel disease
-Other benign
ASA grade (1-4)
Urgency of operation:
-Elective
-Urgent
-Emergent
Procedure performed
Intra-operative
Skin preparation used:
-Chlorhexidine
-Aqueous povidone-iodine
-Alcoholic povidone-iodine
Duration of Surgery (minutes)
Prophylactic antibiotics given:
-Before induction
-During procedure
Degree of contamination:
1. Clean
2. Clean-contaminated
3. Contaminated
4. Dirty
Operation site:
-Large bowel
-Small bowel
-Both
Ostomy:
-Ileostomy
-Colostomy
Mesh used for a hernia? If so, type?

Blood loss (mL)
Wound length (cm)
Number of staples used to close the wound
Type of Prevena used (peel & place Vs customizable)
Post-operative
Overall post-operative complications (Clavien-Dindo Grade ¹⁴)
Removal of VAC early? If so, for what reason?
VAC leakage
Peri-operative transfusion
Surgical site infection: 1-Superficial 2-Deep 3-Organ space -If so, occurred on which day?
Procedures undertaken for SSI: -Opening of wound -Opening the wound and packing -Exploration of the wound under general anesthesia -Application of a vacuum dressing -Oral antibiotics -Intravenous antibiotics
Wound healing Likert Score (1-10) from wound photographs taken on post-operative day 0, 7 and 30

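### The primary endpoint is superficial SSI, but the 80% power rests on an overall SSI rate and is not shown to apply to that endpoint

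*Combined protocol and SAP*

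**What the plan says.** The last paragraph of the Introduction states: "The primary endpoint of this study is the occurrence of superficial SSI within 30 days after surgery". Efficacy outcomes repeats it: "The primary endpoint will be the occurrence of superficial surgical site infection within 30 days after the operation".

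The Statistical analysis section drops the depth:

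- The hypothesis is that "incisional NPWT in adults reduces SSI rates in open, re-operative colorectal surgery".
- The control rate is one the department "has observed a 19.4% overall SSI rate (unpublished internal audit").
- The effect is a 2.34-fold reduction, 19.4% to 8.3%, taken from a retrospective study that the Introduction reports as 29.3% to 12.5%, also without depth.
- The multiplicity sentence reads: "As there is only one primary endpoint (SSI development), adjustments for multiplicity are not required".
- The time-to-event analysis reads: "The log-rank tests will be used to compare the time to first surgical-site infection between the two study groups".

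Appendix 1 records SSI in three classes with the day of onset: "1-Superficial 2-Deep 3-Organ space -If so, occurred on which day". The investigator's verdict at the end of Appendix 2 is a yes/no on whether a patient-reported SSI meets the definition, with no field for depth.

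Deep and organ-space SSI are not listed as secondary endpoints. Efficacy outcomes says: "Secondary endpoints will include length of hospital stay, cost effectiveness, and the clinical efficacy of the device", the last in relation to contamination, comorbidity and operative factors.

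**The concern.** Appendix 1 makes superficial SSI one class of three. A rate for all SSI is therefore at least as high as the rate for superficial SSI, and the two need not respond to the device in the same way. Two things follow.

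First, the stated 80% belongs to the event behind the 19.4% and the 2.34-fold effect. If that event is SSI of any depth, the power for superficial SSI is a different number, which the protocol does not give.

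Second, the event itself is uncertain. Under the endpoint definition, a patient whose only SSI is deep or organ-space is a non-event. Under the wording of the hypothesis, the multiplicity sentence and the log-rank sentence, that patient can be read as an event. An ambiguity of this kind, left open until data by arm are available, lets the definition be chosen with knowledge of the result. The plan schedules a formal interim analysis at 100 patients, so the choice is needed early.

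**Working it through.** **Inputs (Introduction and Statistical analysis).** Control rate 19.4%; source effect 29.3% to 12.5%; intervention rate 8.3%; 149 per arm; two-sided 0.05; power 80%.

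**Step 1: reproduce the plan.** 29.3/12.5 = 2.344, and 19.4/2.34 = 8.29%, as stated. With unpooled variance,

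n per arm = (1.960 + 0.842)² × [p₁(1−p₁) + p₂(1−p₂)] / (p₁−p₂)² = 7.849 × (0.1564 + 0.0761) / 0.111² = 148.1,

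which rounds up to the stated 149. (The pooled-variance form gives 151.) Exact power of the uncorrected chi-square test at 149 per arm is 80.4%. The calculation is sound for the rates entered.

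**Step 2: move to superficial SSI.** Let s be the superficial share of the 19.4%. The documents do not give s, so it is varied as an assumption. The superficial control rate is 0.194s. Power below is exact, for the chi-square test at 149 per arm. The break-even column is the fold reduction in superficial SSI needed to keep 80%.

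| Share s | Control | Control/2.34 | Power at 2.34-fold | Break-even fold |
|---|---|---|---|---|
| 90% | 17.5% | 7.5% | 75.7% | 2.48 |
| 80% | 15.5% | 6.6% | 70.0% | 2.70 |
| 70% | 13.6% | 5.8% | 63.2% | 3.02 |
| 60% | 11.6% | 5.0% | 55.3% | 3.50 |
| 50% | 9.7% | 4.1% | 46.9% | 4.23 |

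**Step 3: the favourable case.** Suppose the whole planned 11.1-point reduction (19.4 − 8.3) falls on superficial SSI.

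- s = 90%: 17.5% against 6.4% (2.75-fold), power 85.9%.
- s = 80%: 15.5% against 4.4% (3.5-fold), power 91.3%.
- s = 70%: 13.6% against 2.5%, power 96%.

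The direction of the error therefore depends on an effect the plan does not state.

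**Step 4: patients whose status is in doubt.** Expected control patients with SSI: 149 × 0.194 = 28.9. If each has one depth class, those without superficial SSI number 28.9 × (1−s) = 2.9, 5.8 or 8.7 at shares of 90%, 80% or 70%. For scale, the planned contrast is 28.9 against 149 × 0.083 = 12.4 events, a difference of 16.5.

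**Step 5: if any SSI were made primary.** The 80% then needs the 2.34-fold effect at every depth. If the device acted on superficial SSI only, the intervention rate would be 0.194(1−s) + 0.194s/2.34, that is 9.4%, 10.5% or 11.6% at shares of 90%, 80% or 70%. Power against 19.4% would be 69.8%, 57.9% or 45.8%.

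**The case against.** The endpoint is formally defined twice, in the same terms, and the later references can be read as shorthand for it. The parenthesis in the multiplicity sentence refers to the only primary endpoint, and the missing-data sentence also speaks of the primary endpoint, which points back to Efficacy outcomes. The log-rank analysis is not labelled primary and could be a supporting analysis of any SSI. The questionnaire serves case finding and asks only about the wound. *Overall* is undefined and might mean across procedures and settings rather than across depths. If the audit rate is superficial-only, the objection to the control rate disappears. The share s is unknown, and a stronger effect on superficial SSI would raise power.

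Much of this stands. The analysis wording is ambiguous rather than explicitly all-SSI, and the log-rank sentence and the questionnaire are the weaker evidence. It would overstate the case to call the 80% wrong or the trial underpowered; *not shown* is the accurate term. The objection does not rescue the figure, though. If the later sections do inherit the superficial definition, the 19.4% and the 2.34-fold effect still have no stated link to superficial SSI. If they do not, the event counted differs. Either reading leaves a defect.

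**Conclusion.** The concern holds and should be fixed before the trial relies on this calculation. The sample-size arithmetic is right for its inputs, but those inputs are not shown to describe the declared primary endpoint. The 80% applies to superficial SSI only if the 19.4% is all or nearly all superficial, or if the reduction in superficial SSI exceeds 2.34-fold by enough to offset the lower base rate. The protocol states neither.

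With the planned effect and assumed shares of 90% down to 50%, power runs from about 76% to 47%. If the full 11.1-point reduction falls on superficial SSI, it is 86% or more at the shares shown. These figures rest on assumed shares and on reading *overall* as all depths, which is the natural reading given Appendix 1 but not a stated one. The ambiguity over which patients are events does not depend on the share; only the number affected does.

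**What to change.** Use one endpoint definition in the Introduction, Efficacy outcomes, Statistical analysis and Appendix 2, fixed before any outcome data by arm are seen. There are two coherent routes.

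- **Keep superficial SSI (the more direct repair).** Replace 19.4% with the audit's superficial-only rate, state the effect assumed on superficial SSI, and restate the power that 149 per arm gives. Say that a deep-only or organ-space-only SSI is not a primary event, and report those by arm beside the primary result. State how an SSI found only by questionnaire is classed.
- **Make any SSI within 30 days primary, with superficial SSI a named secondary.** This matches the hypothesis and, on the natural reading, the sample size. It changes a twice-stated endpoint, so it is a trade-off to be argued. The text should say that 80% then assumes the 2.34-fold effect at all depths, with the step 5 figures as the downside.

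Under either route, name the same event in the log-rank and Kaplan–Meier sentences.

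The cost is wording, one look-up in the internal audit under the first route, and one added item or rule for the questionnaire. Depth is already collected. The restated power may be less favourable, but no extra patients are needed if it is accepted. Holding 80% for superficial SSI at a 2.34-fold effect would need about 168, 192 or 224 per arm at shares of 90%, 80% or 70% (unpooled formula of step 1), that is 38, 86 or 150 more patients than 298.

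### Improvement, not an error: the planned comparison of 30-day superficial SSI is valid but unadjusted, although pre-operative factors are already recorded and no stratification factor is stated

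*Combined protocol and SAP*

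**What the plan says.** The primary endpoint is superficial SSI within 30 days, a yes/no outcome. The Statistical analysis section states: "Descriptive statistical comparisons between the two study groups will be performed with the use of chi-square tests", or Fisher's exact test where appropriate, for categorical endpoints. Time to first SSI is compared by log-rank test. No regression model, covariate or stratified test appears anywhere. The section does not label one test as primary; chi-square or Fisher is inferred from the binary endpoint.

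Under Randomization, patients are "randomly assigned through a concealed centralized secure web based system in a 1:1 ratio"; no stratification or minimisation factor is stated. Allocation is made at the last preoperative visit: "In our department this visit occurs on the day prior to surgery".

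The population is mixed. Study design and patients admits several types of re-operation, among them "intestinal resection with an incisional hernia repair or enterocutaneous fistula repair in both elective and emergency settings".

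Baseline information is already gathered. Procedures says: "Preoperative evaluation will include the prospective assessment and recording of demographic data related to the patient and their co-morbidities". The pre-operative block of Appendix 1 includes "Charleson co-morbidity index" as well as BMI, diabetes, smoking, steroids, albumin, ASA grade and urgency. Intra-operative items come later: "Operative details, including any deviation from allocation, will be recorded immediately after the operation".

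**The concern.** Neither the stated design nor the stated analysis uses baseline risk, although patients differ in operation and urgency and the relevant variables will be in the database. If some of those variables predict SSI, an adjusted analysis estimates the treatment effect more precisely with the same patients and removes the part of any chance imbalance that they explain.

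This matters somewhat more here because the design has little spare power. It sits at 80% with about 41 events expected. The 19.4% control rate is an overall SSI rate, while the endpoint is superficial SSI only, so there may be fewer events. Patients with missing primary data are excluded, and no dropout allowance is stated.

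**Working it through.** **Inputs from the plan.** 19.4% against 8.3%, 149 per arm, 80% power, two-sided 0.05, interim at 100 patients (Statistical analysis).

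**Step 1: the plan's own figure.** Unpooled normal formula: n = (1.960 + 0.842)² × [0.194 × 0.806 + 0.083 × 0.917] / (0.194 − 0.083)² = 7.849 × 0.2325 / 0.01232 = 148.1, so 149 per arm and 298 in total. The stated size is reproduced with no covariates. Exact power at 149 per arm is 80.4% for the uncorrected chi-square and 75.9% for Fisher.

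**Step 2: events.** Final: 149 × 0.194 + 149 × 0.083 = 28.9 + 12.4 = 41.3. Interim: 50 × (0.194 + 0.083) = 13.9. About 41 events support roughly three covariate terms; about 14 support none.

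**Step 3: gain from adjustment.** Prognostic strength is not in the documents. It is assumed here and expressed as the AUC with which three factors together predict SSI. The main simulation (20,000 trials per setting) used BMI as standard normal, diabetes at 20% and a Poisson(2) comorbidity index, with diabetes–comorbidity latent correlation 0 or 0.5, all assumed. It compared the uncorrected chi-square with a standardised risk difference from a logistic model. In the second column both tests are calibrated to exactly 5% (values for correlation 0; 0.5). The third column is a separate run (4,000 trials per setting, Monte Carlo SE about 0.6 points) using the variance factor n/(n−4) = 149/145. The last column is 298 × (1/ratio − 1).

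| Assumed AUC | Power %, crude → adjusted, size-corrected | Power %, crude → adjusted, n/(n−4) | Variance ratio, adjusted/crude | Equivalent patients |
|---|---|---|---|---|
| 0.50 | 79.6 → 79.5; 79.6 → 79.4 | 80.4 → 80.2 | 1.009–1.010 | −3 |
| 0.63 | 79.6 → 80.5; 80.1 → 80.8 | 80.2 → 81.2 | 0.981–0.982 | +6 |
| 0.70 | 80.1 → 82.0; 80.1 → 82.7 | 80.5 → 83.5 | 0.941–0.942 | +19 |
| 0.77 | 79.5 → 84.7; 79.4 → 85.1 | 81.0 → 85.9 | 0.876 | +42 |

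A further simulation with three normal covariates gave variance ratios of 1.015, 0.999, 0.976, 0.952 and 0.915 at AUC 0.50, 0.60, 0.65, 0.70 and 0.74. The pattern is the same, with slightly smaller gains. Urgency was not simulated as such; the gain is driven mainly by the joint AUC.

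**Step 4: type I error.** In the main simulation: crude 4.9–5.2%; adjusted without the variance factor 5.3–5.8%; adjusted with it 4.9–5.5% (Monte Carlo SE 0.15 points). The 4,000-trial run with the factor gave 4.6–5.4%. A 5,000-trial run with the factor gave 4.6–5.9% against 4.4–5.4% crude (SE about 0.3).

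**Step 5: simpler alternative.** Linear regression with HC3 standard errors (10,000 trials): type I error 4.7–5.1%; power 79.2, 80.1, 81.5 and 83.7% against crude 79.7, 79.6, 79.6 and 79.1% at AUC 0.50, 0.63, 0.70 and 0.77.

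**Step 6: fewer events.** If superficial SSI were two-thirds of the overall rate (assumed), the rates are 12.9% against 5.5% and events are 149 × 0.184 = 27. Crude power is 60%, and the size-corrected gains are 0.6, 2.2 and 4.7 points at AUC 0.63, 0.70 and 0.77.

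**The case against.** The strongest reply is that nothing is broken. An unadjusted test of a randomised binary endpoint is legitimate, holds its level, and is what the sample size assumes. That stands, and it is why this is put as an improvement. The gain also rests entirely on assumed AUCs. That stands too: nothing in the documents shows that three routine factors reach 0.77, and with weak factors the gain is under 1 point or a slight loss.

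A second reply is that uncertainty over the test itself matters more. Chi-square and Fisher differ by 80.4 − 75.9 = 4.5 points of power, more than adjustment gains at AUC 0.63 or 0.70. This is correct. It is a reason to name one deciding analysis, which the fix also does; it does not argue against adjusting.

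A third reply is that the adjusted test is slightly liberal. With the variance factor the excess is small, and the HC3 alternative shows none.

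Three stronger readings are tempting and are not supported:

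- A reader might infer that the protocol itself identifies comorbidity as a predictor of SSI. Efficacy outcomes only lists, as a secondary endpoint, "the clinical efficacy of the device in relation to the degree of contamination, patient comorbidity, and operative demographics". Comorbidity is one of three items there, and the question is whether the device effect varies, not whether comorbidity predicts infection.
- A reader might infer that chance imbalance makes the crude test unsafe. In the roughly 4% of null simulated trials where imbalance favours the device by more than 0.2 SD, crude false claims for the device do rise to 5–10% against a nominal 2.5%. In the mirror-image trials they fall to 0–1% (AUC 0.63 to 0.77). The two offset, and the overall level is correct.
- A reader might infer that contamination class, as an obvious risk factor, belongs in the model. It is an intra-operative item, recorded after allocation.

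**Conclusion.** The point holds as a modest, low-cost improvement. The planned comparison is unadjusted, no stratification factor is stated, and usable baseline factors are already recorded. At N = 298, adjustment is worth about 0 power points at AUC 0.50, about 1 at 0.63, 2 to 3 at 0.70 and about 5 at 0.77. The AUCs and covariate distributions are assumptions.

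It would be wrong to conclude that the planned test is biased or invalid, or that the sample size is wrong: 298 is reproduced exactly. Valid here refers only to the absence of adjustment. Complete-case handling and the effect of the interim analysis on the overall error rate are separate questions, and the figures above take the final test at the full 5%.

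**What to change.** Before any outcome data are seen, including the interim at 100 patients, add one paragraph to the Statistical analysis section:

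- The final primary analysis is a logistic model of 30-day superficial SSI on arm plus about three named factors known before randomisation. Examples are BMI, diabetes or comorbidity index, and urgency of operation; the investigators choose. Keep to about one term per factor.
- Report the standardised risk difference with a robust 95% CI and the variance factor n/(n−4), n per arm. Linear regression on the same terms with HC3 standard errors is an acceptable simpler choice. Name one of the two in advance.
- State that this result decides the primary endpoint, and report the crude chi-square beside it.
- Use the crude test at the interim, where only about 14 events are expected.
- Exclude variables recorded during or after surgery, such as contamination class and duration. Exclude Procedure performed if it is settled only at surgery, although Appendix 1 lists it as pre-operative.
- Fill missing baseline covariates by mean or mode, so that the complete-case rule does not remove more patients. With 5% missing per covariate, simulated power was 81.3, 83.1 and 85.6% against 81.5, 83.2 and 85.7% with full data (AUC 0.63, 0.70, 0.77, without the variance factor).

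Cost: no new data and no more patients. Covariates must stay few with about 41 events or fewer, there may be almost no gain if the factors are weak, type I error may reach about 5.5% with the standardised estimate, and standardisation may need software beyond the SPSS version named in the plan.

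### The formal interim analysis at 100 of 298 patients has no stated purpose, efficacy boundary or alpha allocation, so the plan does not secure its two-sided type I error of 0.05

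*Combined protocol and SAP*

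**What the plan says.** The interim analysis is covered by one sentence, at the end of the Statistical analysis section: "A formal, interim analysis is planned to take place when a total of one hundred patients have been accrued for both arms all together". Nothing else in the documents describes its purpose, endpoint, test, threshold or consequences.

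The surrounding text of that section supplies these rules:

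- **Significance.** A single threshold of P<0.05, stated immediately before the interim sentence, with no distinction between interim and final analysis.
- **Test.** For binary outcomes, chi-square or Fisher's "exact test, as appropriate, for categorical end points".
- **Sample size.** For a fall in the infection rate from 19.4% to 8.3%, 298 patients (149 per arm) "are required to achieve a power of 80% and a two-sided type I error rate of 0.05".
- **Multiplicity.** "As there is only one primary endpoint (SSI development), adjustments for multiplicity are not required".

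The primary endpoint is superficial SSI within 30 days. Under Procedures, "A second formal wound review will be performed at 30 (+/-7) days".

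**The concern.** A plan that claims a 5% error rate and schedules a formal look at about a third of the patients needs a rule connecting the two, and none is given. The multiplicity sentence concerns the number of endpoints and does not cover testing the same endpoint twice. As written, an analyst could test SSI at 100 patients, find P<0.05 and report success, or continue and test again at 0.05.

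Two things are at stake if that happens. The chance of a false claim in favour of the device rises from a nominal 2.5% to between 4.2% and 4.6% by chi-square (half of the two-sided exact error). And an early claim based on about 50 patients per arm would, on average, overstate the benefit considerably.

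A smaller point is that the trigger counts patients accrued, whereas the endpoint is complete only after the day-30 review. The number of outcomes available at the look is therefore undefined.

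**Working it through.** **Inputs.** From the Statistical analysis section: rates 19.4% and 8.3%, two-sided alpha 0.05, power 80%, 149 per arm, interim at 100 patients. From Randomization: 1:1 allocation, so about 50 per arm at the interim.

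**1. Reproduce the planned size.** Two proportions, unpooled variance:

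n = (1.960 + 0.842)² × [0.194 × 0.806 + 0.083 × 0.917] / (0.194 − 0.083)² = 148.1, rounded up to 149 per arm, or 298.

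This matches the plan and is a fixed, single-look calculation. It contains no allowance for an interim test.

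**2. Error if P<0.05 is used at both looks (normal theory).** Assume all 100 patients have complete 30-day outcomes. The information fraction is 100/298 = 0.336, and the correlation between the interim and final statistics is √0.336 = 0.579. Then

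P(|Z₁| > 1.96 or |Z₂| > 1.96) = 0.0883.

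**3. The same by exact calculation.** Enumerate binomial outcomes at 50 + 50, carry the non-rejected ones forward with a further 99 + 99 patients, and test at 149 + 149. The mixed rule uses Fisher when an expected count is below 5, which is an assumed reading of the plan's choice of test. Overall two-sided error:

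| Common SSI rate | Chi-square | Fisher, both looks | Mixed rule |
|---|---|---|---|
| 8.3% | 8.5% | 4.2% | 7.0% |
| 10% | 8.9% | 4.7% | 8.0% |
| 14% | 9.2% | 5.2% | 9.1% |
| 19.4% | 9.1% | 5.8% | 9.1% |

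For comparison, a single final Fisher test has an error of 3.1% to 3.6%. Under the mixed rule, Fisher is selected at the interim in 68%, 45%, 9% and 0.4% of trials respectively.

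**4. Effect of counting accrued patients.** Assume even accrual over the planned 36 months: 298/36 = 8.3 per month. About 10 of the 100 would then not have reached day 37. A fraction of 90/298 = 0.302 gives 8.9%, and a fraction of 0.25 gives 9.1%. The error rate hardly depends on this.

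**5. Exaggeration under the planned effect.** With true rates of 19.4% and 8.3% (difference 11.1 points), the interim gives P<0.05 in 38% of trials by chi-square, with a mean observed difference of 17.8 points. By Fisher the figures are 25% and 19.6 points.

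**6. Example boundaries.**

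- *Haybittle-Peto* (interim P<0.001, final P<0.0495): overall error 5.00% by normal theory, 4.80% to 5.05% by exact chi-square, and 3.06% to 3.52% by exact Fisher.
- *O'Brien-Fleming-type*: spending the two-sided 0.05 directly gives 2 − 2Φ(1.96/√0.336) = 0.0007 at the interim and 0.0497 at the end, overall 5.00%. Spending 0.025 on each side gives 0.0002 and 0.0499, which also holds 5%. The two pairs differ only in convention.

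Exact power at 298 patients:

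| Test | Single look | Haybittle-Peto | O'Brien-Fleming-type (0.0007/0.0497) |
|---|---|---|---|
| Chi-square | 80.40% | 80.42% | 80.41% |
| Fisher | 75.91% | 75.89% | 75.88% |

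**The case against.** The strongest reply is that the harm is conditional. No sentence says that the interim tests the primary endpoint, uses P<0.05 or can stop the trial. A look for safety, futility or description would not inflate the error. On this view the documents show under-specification and not an inflated error rate. That is correct as far as it goes, and it is why the point is that 0.05 is not secured. But the look is called formal, it follows directly on the only significance rule, and no text confines it to a purpose that would be harmless.

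Second, Fisher's test is permitted, and with Fisher at both looks the error stays below 5% at rates of 8.3% and 10%. The 19.4% is also an overall SSI rate, while the endpoint is superficial SSI, so the lower rates may be the relevant ones; the documents give no superficial-only rate. This narrows the problem without removing it. The choice of test is left open, chi-square gives 8.5% even at the lowest rate, and the mixed rule gives 7.0% there.

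Third, a boundary does not cure exaggeration. Under Haybittle-Peto with the planned effect, only 2.8% of trials cross at the interim by chi-square, but the mean observed difference in those is 26.3 points. This stands: a strict boundary makes such claims rare, but the estimate at a crossing is no less exaggerated.

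Fourth, by exact chi-square the small cut in the final threshold makes almost no difference once the interim level is 0.001. This also stands. What matters most is a stated purpose and interim rule.

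**Conclusion.** The concern holds, and the plan should be corrected before any interim data are seen. The omission is certain: a formal look is scheduled with no rule, beside a claim of "a two-sided type I error rate of 0.05" that rests on a single-look sample size.

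The size is conditional on testing the primary endpoint at P<0.05 at both looks, with either able to support an efficacy claim. The overall two-sided error is then 8.8% by normal theory. By exact calculation it is 8.5% to 9.2% with chi-square, 7.0% to 9.1% with the mixed rule and 4.2% to 5.8% with Fisher throughout. The exact figures assume 50 + 50 and 149 + 149 complete outcomes and common SSI rates of 8.3% to 19.4%. The accrued-versus-assessed ambiguity needs clarifying but hardly changes the error rate.

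**What to change.** Before interim data are seen, add to the Statistical analysis section:

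1. The purpose of the interim, its endpoint and its test, and whether it takes place once 100 patients have their day-30 outcome.
2. One of two rules:
   - (a) an efficacy boundary, for example Haybittle-Peto (interim claim only if P<0.001, final test at two-sided P<0.0495) or an O'Brien-Fleming-type rule (0.0007 and 0.0497, naming the spending convention); or
   - (b) a statement that no efficacy claim will be made at the interim, with 0.05 kept for the final test.
3. A reworded multiplicity sentence that covers multiple endpoints only and refers to the interim rule for repeated looks.

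The choice between (a) and (b), and of boundary, is the sponsor's. The cost is two or three sentences and no extra patients. Under (a) the final threshold falls to 0.0495 or 0.0497, with power unchanged at 80.4% by chi-square and 75.9% by Fisher. Option (b) has no statistical cost.
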